**Research Objectives / Specific Aims / Outcome Measures:**

**Objective:** To determine if debridement improves healing time for secondary intention wounds.

**Hypothesis** Aggressive and frequent debridement of an acute post-surgical wound shortens healing time.

**Outcomes Measures** The primary outcome measure will be time to healing. Secondary outcomes will include patient satisfaction with their scar (as assessed by the Patient Scar Assessment Questionnaire) at time of complete healing, cosmetic appearance (Visual analog Scale) as rated by a blinded reviewer at time of complete healing, number of required debridements by time of complete healing, treatment failures at week 16, and number of complications (including pain, bleeding, infection, tumor recurrence) by time of complete healing or by week 16.

The Patient Scar Assessment Questionnaire is a validated questionnaire used standardly in Dermatology for assessing patient-based outcome measures of scarring. It consists of 5 subscales: appearance, symptoms consciousness, satisfaction with appearance and satisfaction with symptoms. Each subscale consists of a set of items with 4-point categorical responses, scoring 1 to 4 points (with 1 point assigned to the most favorable category and 4 assigned to the least favorable). It has been demonstrated to be a reliable and valid measure of patients' perception of scarring.

The Visual Analog Scale is a validated image-based scale that is frequently used in the Dermatology and Plastic Surgery literature, that uses

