**Study Design / Procedures:**

Randomized Clinical Trial

**Enrollment** At the baseline visit, after the patient has signed consent and been randomized to their specific treatment arm, we will obtain basic demographic information including age, sex and race, as well as pertinent comorbidities that would affect wound healing such as diabetes, venous stasis, immunosuppression and tobacco use (if documented as problems in the patient's chart). Wound defect width, length, and depth will also be measured at baseline, prior to any intervention.

**Intervention Arms:** 1) Aggressive debridement: Aggressive and frequent debridement of fibrin and crust from the wound base down to pinpoint bleeding, both by the patient as part of daily wound care at home, and also by the clinician (either physician or experienced dermatologic surgery nurse) during follow-up visits. Silver nitrate will be used to treat excessive granulation tissue only if the granulation tissue is higher than the level of surrounding skin. Patients will return weekly until healed. Patients will be provided with detailed instructions and guidelines to help determine whether healing has taken place.

2) Minimal debridement: No debridement of fibrin by the patient or the clinician. Exceptions include debridement of dried crust or eschar. Silver nitrate will be used to treat excessive granulation tissue only if the granulation tissue is higher than the level of surrounding skin. Patients will return every two weeks until healed. In between visits at weekly intervals, the patient will be contacted by phone to determine if healing has occurred in between clinic visits. Patients will be provided with detailed instructions and guidelines to help determine whether healing has taken place.

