**Notes:**

- The following information will be recorded for each patient at each clinic visit for both treatment arms, using a standardized data collection form: Date of follow up; pain (0/10); episodes of bleeding (# and whether mild, moderate, or severe); amount of crust (mild, moderate, or severe); amount of fibrin (mild, moderate, or severe); size

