**Study Title: Prospective randomized clinical trial comparing outcomes of secondary intention wound care methods**

of wound (width, length, and depth); whether the wound is completely healed (completely re-epithelialized); any tumor recurrence (as determined by physician); if excess granulation tissue is present (as determined by being higher than the level of the surrounding skin); if there is infection (as determined by the physician); whether culture was taken; and degree of debridement (none, mild, moderate, or severe).

- At each visit, we will review the treatment method with the patient (i.e. whether aggressive or minimal debridement), reinforce the instructions, and give them another written copy of their wound care methods)
- We will measure time to 50% healing of the wound for all patients.
- *Both intervention arms (aggressive debridement and minimal debridement) are accepted methods of post-operative care for secondary intention wounds. While both methods are practiced at Lahey Clinic, there is no known, published “standard-of-care” in the literature for such wounds. This is because there have been no randomized controlled trials undertaken comparing efficacy of these two methods. That is the purpose of this study.*
- *It is the standard of care to have patients with wounds healing by secondary intention return to clinic for wound checks until the wounds is sufficiently healed; however, the exact interval period is up to the discretion of the provider. In this study, we will be following up weekly with patients receiving frequent debridement and biweekly with patients receiving minimal debridement. All patients will continue to be followed until their wounds are healed.*

Ongoing Care: The patient will return to clinic for evaluation until defect is completely healed, as determined by the principal investigator.

The follow-up intervals are as noted above.

- Patients will be asked to record the date on which their wound healed, and this will be reviewed over the phone or at their next clinic appointment.

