**Statistical Analysis:**

Analytic Plan

Differences in demographic and wound characteristics between groups will be compared to evaluate balance between groups. Differences between treatments arms for the primary (time-to-healing) and continuous secondary outcomes (patient satisfaction with their scar, cosmetic appearance, number of complications) will be analyzed using t-tests for independent groups. If time-to-healing is not distributed normally, or if there are censored observations (e.g., loss to follow-up, or not all patients have healed by the 16-week endpoint), a log-rank test will be used to test for differences in

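### Complications are collected on a visit form completed weekly in one arm and every two weeks in the other, so at equal follow-up visit frequency can raise the aggressive arm's count

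*Combined protocol and SAP*

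**What the plan says.** The Outcomes Measures paragraph lists as a secondary outcome the "number of complications (including pain, bleeding, infection, tumor recurrence) by time of complete healing or by week 16". The Analytic Plan puts it among the "continuous secondary outcomes (patient satisfaction with their scar, cosmetic appearance, number of complications" and compares it by a t-test for independent groups, with no adjustment for visits or follow-up time.

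The data source is set out in the Notes under Study Design / Procedures: "The following information will be recorded for each patient at each clinic visit for both treatment arms". The items include "pain (0/10); episodes of bleeding (# and whether mild, moderate, or severe", and later "if there is infection (as determined by the physician" and tumor recurrence. The form is not reproduced.

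The same Notes describe "following up weekly with patients receiving frequent debridement and biweekly with patients receiving minimal debridement"; Intervention Arms and the Study Calendar agree. In the minimal arm's off-weeks, "the patient will be contacted by phone to determine if healing has occurred in between clinic visits". Patients also "record the date on which their wound healed, and this will be reviewed over the phone" or at the next appointment. Neither contact is described as covering complications.

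Anticipated Limitations recognises that the unequal schedule could distort the ascertainment of healing time and offers the calls as protection. It says nothing comparable about complications. Potential Risks and Discomforts anticipates more bleeding and pain in the aggressive arm.

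**The concern.** The outcome is a count, and one arm has twice as many scheduled occasions on which the count can rise. The protocol accepts this mechanism for healing time and guards against it there, but leaves it open for complications.

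Three gaps let visit frequency into the count. Bleeding is a number of episodes, but the protocol does not say since when. Nothing says how a pain score or an infection present at successive visits is counted. And the off-week contact that could equalise collection is not described as asking about any of this.

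More frequent recording pushes in the same direction as the anticipated harm. A higher count in the aggressive arm could then be real harm, more frequent looking, or both, and a t-test on the raw count does not separate them.

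**Working it through.** **The plan's own figure.** The documents give no figure for complications. The only calculation is for healing time: difference 14 days, SD 15 days, two-sided alpha 0.05, 80% power. The t-based solution is 19.03, rounded up to 20 per arm, with 82.0% power at 20. It reproduces, and this point does not touch it.

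**Inputs.** From the documents: 20 per arm, SD 15 days, visits every 7 or 14 days, 16-week limit, two-sided t-test at 0.05. Assumed, because the documents give none: mean healing of 42 days in both arms, complication rates, episode durations, recall, and between-patient variation. Healing times were drawn from a normal distribution limited to 7-112 days, and the true risk was equal in both arms.

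**Forms per patient.** By week 16 the schedule allows 16 forms against 8. At 42 days, rounding up to the next visit adds on average half an interval: 6 + 0.5 = 6.5 forms against 3 + 0.5 = 3.5.

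**Full recall, each episode counted once.** The expected counts are equal, and simulated false rejection is about 5%.

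**Fading recall.** Suppose an episode d days before the visit is reported with probability 0.5^(d/h). Let x = 0.5^(7/h). The ratio of average capture, weekly to two-weekly, is 2/(1 + x).

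| Half-life h | x | Capture ratio | False rejection at 0.1-0.3 episodes per week, equal patient risk |
|---|---|---|---|
| 14 days | 0.71 | 1.17 | 6-9% |
| 7 days | 0.50 | 1.33 | 8-16% |
| 3.5 days | 0.25 | 1.60 | 12-26% |

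With gamma-distributed patient rates the 3.5-day row falls to about 9-13%, and the overall range to about 5-13%. Milder variation would lie between the two sets.

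**Persistent episodes, seen only if present at a visit.** Counted once, at 0.02-0.3 per week: 2-21% for a mean duration of 1 week and 3-12% for 2-4 weeks. Counted again at every visit: about 12-14% at 0.1 per week and 34-37% at 0.3. The protocol does not say which rule applies.

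**Extreme: no recall and no persistence.** The expected count is p times the number of forms; at p = 0.1, 0.65 against 0.35. False rejection is 14%, 26%, 49% and 68% at p = 0.05, 0.1, 0.2 and 0.3. If p varies strongly between patients (beta distribution, alpha + beta = 2), these become about 4%, 9%, 20% and 34%.

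**If the aggressive arm heals 14 days sooner** (42 against 56 days, 0.1 episodes per week). The true totals are 0.1 × 6 = 0.60 and 0.1 × 8 = 0.80. With episodes counted once if present at a visit, the recorded totals are:
- mean duration 4 weeks: 0.53 against 0.62;
- 2 weeks: 0.47 against 0.49;
- 1 week: 0.37 against 0.33, which is reversed.

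In terms of recall, if a share r of the minimal arm's off-week episodes is reported, its total is 0.80 × (1 + r)/2. This equals 0.60 at r = 0.5. The simulated break-even is 45-56%, depending on how the last interval is handled.

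**With weekly contact in both arms.** Under the same fading-recall cases, false rejection returns to 4.7-5.3%, assuming a phone answer captures as much as a visit.

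**The case against.** The strongest reply has four parts.

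First, a reader might infer that complications have no counting rule at all. The documents do not support that. Bleeding is recorded as a number of episodes, recurrence is naturally yes or no, and an episode count on a serial form is ordinarily read as episodes since the last visit. On that reading, with full recall, there is no inflation. The form is not reproduced and may carry look-back wording, so one can say only that the protocol does not state it. This stands and narrows the gap to the unstated look-back, incomplete recall, and repeated pain or infection entries.

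Second, every rate, duration and recall value is assumed, and equal risk for all patients inflates the upper figures. This also stands. The percentages are illustrations, not estimates for this trial.

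Third, weekly visits with clinician debridement are part of the aggressive regimen, so pain or bleeding provoked there is a real effect. True, but the concern is different: events between visits that only the more frequent form picks up.

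Fourth, the form is dated, so some alignment is possible at analysis. That is correct for findings present at a visit, and the fix uses it. It cannot recover off-week events that nobody asked about.

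**Conclusion.** The point holds. As written, complications are ascertained at twice the frequency in one arm, and the safeguard adopted for healing time does not extend to them. At equal follow-up this can raise the aggressive arm's recorded count.

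The size runs from essentially none with full recall, through about 5-13% false rejection with fading recall and varying patient risk, to 6-26% with fading recall and equal risk. The no-recall figures of 14-68% are an extreme, falling to about 4-34% with strong between-patient variation. All rest on an assumed 42-day mean healing time and on assumed rates.

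Two stronger conclusions a reader might draw are not supported. One is that the planned test will produce a false harm signal: with good recall it need not. The other is that visit frequency would reverse the comparison if the aggressive arm heals sooner. Shorter exposure offsets the extra recording, and in the cases above the usual result is a smaller apparent advantage; reversal needs episodes of about a week or poor off-week recall.

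Only this secondary outcome is affected. The change is worth making because off-week information that is never asked for may not be recoverable later.

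**What to change.** - **Study Design / Procedures.** Use the minimal arm's planned off-week call to ask the same pain and bleeding questions as the visit form, and to ask about suspected infection. In both arms, record events since the last contact and count a continuing episode once.
- **Analytic Plan.** Add a sensitivity analysis using only even-week forms in both arms for findings present at a visit (pain score, infection). Stop at the healing date in both arms. Otherwise a wound that heals in week 5 gives two even-week forms in the aggressive arm (weeks 2 and 4) but can give three in the minimal arm (weeks 2, 4 and 6).
- **Anticipated Limitations.** State that physician-judged infection is still examined more often in the aggressive arm, and that a phone answer may capture less than a visit.

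The cost is slightly longer calls and a little more analysis, with no extra visits or patients. A small imbalance for infection remains: false rejection of about 2-7% at an assumed 0.02-0.05 infections per week lasting 1-4 weeks.

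### The pooled complication count does not separate the pinpoint bleeding that aggressive debridement intends from bleeding as a complication, so an excess in that arm could not be read as harm

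*Combined protocol and SAP*

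**What the plan says.** Four parts of the combined protocol and SAP bear on this.

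- **Outcome Measures** lists as a secondary outcome the "number of complications (including pain, bleeding, infection, tumor recurrence) by time of complete healing or by week 16". Bleeding appears without a severity threshold.
- **Study Design / Procedures, Intervention Arms** describes the aggressive arm as "Aggressive and frequent debridement of fibrin and crust from the wound base down to pinpoint bleeding", done "both by the patient as part of daily wound care at home, and also by the clinician" at follow-up visits. For the minimal arm it says "No debridement of fibrin by the patient or the clinician. Exceptions include debridement of dried crust or eschar".
- **Study Design / Procedures, Notes** has the visit form record "episodes of bleeding (# and whether mild, moderate, or severe", in both arms. Pain (0 to 10), infection, tumor recurrence and degree of debridement are separate items on the same form.
- **Statistical Analysis, Analytic Plan** states that "continuous secondary outcomes (patient satisfaction with their scar, cosmetic appearance, number of complications) will be analyzed using t-tests for independent groups".

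No section says whether bleeding produced by a debridement is an episode, which grade makes a bleed a complication, or how pain, bleeding, infection and recurrence become one number.

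**The concern.** In one arm, following the assigned procedure produces an event of the same name as a component of the harm outcome. Whether that event is counted is left to whoever fills in the form or builds the analysis variable, and neither patients nor providers are blinded. The problem would remain with identical visit schedules and perfect recall. The weekly versus two-weekly recording adds to it in the same direction but is a separate matter.

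This count is the only planned between-arm comparison of complications, and there is no formal data safety monitoring board. Both methods are accepted practice at the site, so a difference that is hard to interpret could still influence which one is preferred. Pooling adds a second difficulty. Infection and recurrence are likely to be few, so a common minor event in the same sum can dominate them.

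**Working it through.** **The plan's own figure.** The documents give no number for the complication outcome. The sample size, for time to healing, reproduces: with a difference of 14 days, SD 15, two-sided alpha 0.05 and 80% power, the noncentral t solution is 19.03 per arm, rounded up to 20. Power at 20 per arm is 82.0%. Nothing below changes it.

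**Inputs for the illustration.**

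- From the documents: n = 20 per arm; two-sided t-test at 0.05; daily home debridement plus one weekly clinic debridement, so 7 + 1 = 8 per week; SD of healing time 15 days, so s = 15/7 = 2.14 weeks.
- Assumed: mean healing time w of 4 to 6 weeks; mean m of other complications, equal in both arms, from 0.5 to 4 per patient; fraction f of intended bleeds recorded as episodes of 1%, 2% or 5%; no such bleeds recorded in the minimal arm.

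**Formulas, with Poisson background counts.**

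- Shift in mean = 8·w·f
- Variance, aggressive arm = m + 8·w·f·(1−f) + (8f)²·s²; variance, minimal arm = m
- SE = √[(sum of the two variances)/20]
- Probability of significance ≈ Φ(shift/SE − 2.02), where 2.02 is the critical t on 38 df

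**Base case, w = 6 and m = 1.** There are 8 × 6 = 48 intended bleeds per patient.

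| f | Shift | Variance, aggressive | SE | Shift/SE | Approximation | Simulation |
|---|---|---|---|---|---|---|
| 0 | 0 | 1.00 | 0.316 | 0 | 5% | 4.7% |
| 1% | 0.48 | 1.50 | 0.354 | 1.36 | 25% | 26% |
| 2% | 0.96 | 2.06 | 0.391 | 2.46 | 67% | 68% |
| 5% | 2.40 | 4.01 | 0.501 | 4.79 | >99% | 99.9% |

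The f = 0 approximation counts both tails. Simulations used 4,000 trials per setting.

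**Swamping.** In this case, procedural bleeds make up 0.96/1.96 = 49% of the aggressive arm's mean count at f = 2%, and 2.40/3.40 = 71% at f = 5%.

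**Range.** This covers Poisson backgrounds with m from 0.5 to 4 and w from 4 to 6, plus an overdispersed background (gamma-mixed, shape 0.5) with m = 2 and w = 6. The test is significant in about 8–41% of trials at f = 1%, 18–85% at 2% and 63–100% at 5%. A further run of the same model crossed all the settings. The least favourable combination (m = 4, shape 0.5, w = 4) gave about 5%, 6% and 17%, so the lower ends are not floors.

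**A narrower model.** Suppose only clinic debridements can generate a recorded episode, with 6 weekly visits and m = 1. The test is then significant in 13%, 37% and 96% of trials if 5%, 10% and 25% of those bleeds are recorded. Over 4 to 8 visits and m from 0.5 to 2, the ranges are 8–31%, 13–78% and 52–100%.

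**The case against.** The strongest reply is that the plan never says pinpoint ooze counts. Outcome Measures gives no counting rule. The visit form also records crust, fibrin and wound size, which nobody would call complications, so being on the form does not make a mild bleed one. A reader might infer that bleeding of any severity is counted, but that is drawn from silence. This part of the reply stands. What remains is that the rule is missing and could be settled after data are seen.

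A reader might also infer that the comparison reflects the procedure and not harm. The documents do not support that. Potential Risks and Discomforts names more bleeding, pain and scarring as possible side effects of aggressive debridement, and bleeding beyond the intended depth is a real treatment effect that the trial should be able to show. The count also contains pain, infection and recurrence. Nor is the minimal arm free of procedural bleeding by design, since dried crust or eschar may be debrided there.

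The rejection rates are illustrative. Adding events to one arm must raise them, and the recording fraction, background rate and healing time are all assumed. They are not an inflated type I error in the strict sense: if those bleeds count, the arms do differ on the outcome as defined. The difficulty is what that difference would mean.

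Finally, the form already collects grades and components. That makes the remedy easy, but the Analytic Plan still names only the pooled number.

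**Conclusion.** The point holds in this form: as written, the pooled count cannot distinguish intended pinpoint bleeding from bleeding as a complication, so an excess in the aggressive arm would not be interpretable as harm. That conclusion comes from the text and needs no simulation. How large the effect would be is uncertain. Recording a few percent of intended bleeds could make a significant difference likely with all else equal, but under a high and strongly overdispersed background the effect could be small. One secondary outcome is affected. This is a cheap improvement, not a threat to the trial's main result.

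**What to change.** - In Outcome Measures and in the Notes on the visit form, state that pinpoint bleeding produced by a debridement and confined to it is not counted as a complication, in either arm.
- Record such bleeding on a separate line of the form.
- In the Analytic Plan, compare bleeding (by the grade already recorded), pain, infection and tumor recurrence as separate components, not only as a sum.
- Report bleeding by grade both with and without procedural bleeds.

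The change costs a sentence in the outcome definition, a matching note and one split line on the form, and a revised line in the analysis. Treatment, visits and sample size stay as they are. The main downside is that unblinded staff and patients must judge whether a mild bleed was procedural, and most debridements happen at home. Reporting bleeding both ways shows how far the result depends on that judgement. Four component comparisons also mean more tests: if independent and each at 0.05, the chance of at least one false positive is 1 − 0.95⁴ = 18.5%, so they are best presented as descriptive estimates with confidence intervals.

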**Statistical Issues**

Sample Size/Power	Time to healing will be the primary outcome measure and will be compared between groups using a two-sided t-test. There is limited literature regarding similar patients to help guide estimates for a power analysis. Based on a review of the literature,  and a brief review of patients previously seen at our clinic, we powered the study to detect a difference in healing time between treatment groups of 14 days, and assumed a standard deviation (SD) of 15 days. To obtain 80% power to detect such a difference, assuming alpha=0.05 and a two-sided t-test, 20 patients per group (40 total) are required.
Anticipated Strengths	We performed a priori power analysis. We are using a randomized study design with validated survey instruments. We plan to use a blinded reviewer of the final cosmetic outcome.
Anticipated Limitations	Given the nature of our study, it will not be possible to conceal treatment arm to patients or providers, though assessment of the final outcome will be by blinded reviewer. If variability in wound healing is greater than anticipated, we may not have statistical power to detect differences between groups; however, the estimates we obtain will help inform future studies. The minimal debridement group will be seen by the clinician every two weeks; while the aggressive debridement group will be seen weekly. It is therefore possible that ascertainment of time to wound healing will differ between groups. However, we hope to avoid this bias checking with the minimal debridement group by phone on weeks where they have no scheduled visit.

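### Complications are counted only to healing or week 16, so time at risk is set by the primary outcome, and the planned t-test on raw counts cannot separate risk from length of observation

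*Combined protocol and SAP*

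**What the plan says.** Under Research Objectives / Specific Aims / Outcome Measures, "The primary outcome measure will be time to healing", and one secondary outcome is the "number of complications (including pain, bleeding, infection, tumor recurrence) by time of complete healing or by week 16".

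Under Statistical Analysis, "continuous secondary outcomes (patient satisfaction with their scar, cosmetic appearance, number of complications) will be analyzed using t-tests for independent groups". That section gives no rate, exposure offset, common window or time-to-first-event analysis for complications.

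Follow-up ends at healing. Under Ongoing Care, "The patient will return to clinic for evaluation until defect is completely healed, as determined by the principal investigator". The Study Calendar says the same for each arm. Apart from the contact at which the healing date is reviewed, nothing is scheduled after healing. Data collection past week 16 applies only to wounds still open then.

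Safety items are recorded at visits: "The following information will be recorded for each patient at each clinic visit for both treatment arms". The schedules differ. For the aggressive arm, "Patients will return weekly until healed"; for the minimal arm, "Patients will return every two weeks until healed". The minimal arm's off-week phone calls are described only as a check on healing.

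Under Statistical Issues, "we powered the study to detect a difference in healing time between treatment groups of 14 days". The limitations there discuss unequal ascertainment of healing time, but not unequal time at risk for complications.

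**The concern.** The event that closes the complication count is the event the trial hopes to bring forward. If the arms differ in healing time, as the power calculation supposes, they are watched for harm for different lengths of time. A comparison of raw counts then mixes two questions: how often complications occur while a wound is under treatment, and how long that treatment lasts.

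The mixing bears on a harm the protocol itself anticipates. Potential Risks and Discomforts names bleeding and pain as possibly more common with aggressive debridement, while the hypothesis expects that arm to heal sooner. A higher weekly rate could be offset by a shorter window and leave the counts level.

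Tumor recurrence is the least suited to this window, because its risk does not end when the skin closes. A patient healed at week 4 contributes 4 weeks of observation for recurrence; a slow healer contributes up to 16.

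**Working it through.** **Inputs from the documents (Statistical Issues; Study Design / Procedures).** Difference 14 days, SD 15 days, 20 per arm, two-sided alpha 0.05, power 80%, cap at 16 weeks (112 days), visits every 1 or 2 weeks.

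**Inputs assumed, because the documents give none.** Mean healing time in the faster arm (m): 30, 42 or 60 days. Weekly complication rate: 0.02 to 1 per patient, the same in both arms and constant until healing. Counts are Poisson.

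**1. The plan's own figure.** n per arm = 2 × (1.960 + 0.842)² × 15² / 14² = 18.02, so 19 by the normal approximation. Exact t-test power is 79.9% at 19 per arm and 82.0% at 20. The planned 20 per arm reproduces.

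**2. Excess count from exposure alone.** Expected count = weekly rate × weeks to healing, so at equal rates the slower/faster ratio is about (m + 14)/m:
- 44/30 = 1.47 (1.45 once healing times are limited to 7–112 days)
- 56/42 = 1.33
- 74/60 = 1.23

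**3. How often the planned t-test rejects at equal weekly rates.** 20,000 simulated trials per scenario, 20 per arm, healing times Normal(m, 15) against Normal(m + 14, 15), limited to 7–112 days:

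| Weekly rate | m = 30 | m = 42 | m = 60 |
|---|---|---|---|
| 0.25 | 22% | 19% | 15–16% |
| 0.5 | 34% | 30% | 25% |
| 1.0 | 49% | 44% | 37% |

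At lower rates, across the same three means, rejection is about 5% to 6% at 0.02 per week, 7% to 8% at 0.05 and 9% to 13% at 0.1. With gamma healing times (means 28 to 70 days in the faster arm) and rates of 0.05 to 0.5, the t-test finds significantly fewer events in the faster arm in 6% to 38% of trials, against 2.5% expected in that direction. A comparison per patient-week on the same data rejects in 4.8% to 5.3%.

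**4. Masking.** Take 42 against 56 days, that is 6 against 8 weeks. A slower-arm rate of 0.25 per week gives 0.25 × 8 = 2.0 events. A faster-arm rate one third higher gives 0.25 × (4/3) × 6 = 2.0. The mean counts are equal although the weekly rates are not.

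**5. Sensitivity to constant risk.** If risk halves every 14 days after surgery (illustrative, 1 to 2 expected events), the excess count falls to between about 18% (m = 30) and 4% (m = 60), and rejection to about 5% to 10%.

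**6. Recording frequency.** Suppose an item is scored once per visit, with equal probability at each visit, and the aggressive arm heals at 42 days against 56. Mean visits are 6.5 (weekly) against 4.5 (two-weekly), a ratio of 6.5/4.5 = 1.44 with the faster arm higher. Across scenarios the ratio is 1.3 to 1.6. Per week observed it becomes (6.5/6)/(4.5/8) = 1.9, further from 1. If the minimal arm heals faster, it has only 0.38 to 0.44 times as many visits, which adds to the exposure effect.

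**The case against.** **The count to healing is a legitimate outcome.** If slower healing brings more complications, patients do bear more of them, and a t-test that detects this is not wrong about the outcome as defined. This stands. The rejections in step 3 are not false positives for total burden; they mislead only if read as a difference in risk.

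**The direction is not fixed.** A reader might infer that the faster-healing arm must look safer. The documents do not support that. Items scored once per visit have more recording opportunities in the aggressive arm, which can offset or reverse the exposure effect if that arm heals first. The plan does not say how a complication is counted, so the net effect cannot be signed. With few events, chance can also hide it.

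**A simple per-week rate is not a full remedy.** Step 6 shows that it worsens the comparison for per-visit items. This stands and limits the fix.

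**The larger percentages need high event rates.** One event per week is about 8 per patient over 56 days. At rare-event rates, or with risk concentrated early, the effect is small.

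**Week 16 may be meant as a second, fixed time point.** The wording allows it, and a reader should not infer that later events were ruled out by design. But no visit is scheduled after healing to collect a week-16 count, so in practice a healed patient's count stops at healing.

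**Conclusion.** The concern holds in a limited form. The window for counting complications is tied to the primary outcome, and the analysis has no allowance for it. Under the plan's 14-day difference and equal constant weekly risk, exposure alone gives the slower arm about 23% to 45% more events. The effect on the t-test ranges from negligible (5% to 8% rejection at 0.02 to 0.05 events per week) to substantial (about 15% to 49% at 0.25 to 1). Mean healing times, event rates, constant risk and Poisson counts are all assumptions.

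What can be concluded is that the planned comparison cannot separate risk from duration, and that unequal recording blurs it further. It cannot be concluded which arm will be flattered. This is a secondary outcome, but the trial's safety comparison rests on it and the remedy is cheap, so the change is worth making.

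**What to change.** 1. In Outcome Measures, say whether week 16 is a cap or a second time point, and define what counts as one complication. Keep the count to healing, labelled as total burden.
2. In Statistical Analysis, add an exposure-adjusted comparison for distinct, onset-dated events such as bleeding episodes and infections: Poisson or negative binomial regression with log weeks observed as offset, using dates already collected. Ask about these events on the minimal arm's existing off-week calls as well, so that both arms have weekly recording opportunities.
3. Do not apply the per-week rate to items scored once per visit, such as the 0–10 pain score. Compare these at the two-weekly visits common to both arms, and show how many patients are still under observation at each.
4. State that tumor recurrence is assessed over one common window, surgery to week 16, for every patient, by a chart check or one call for those already healed.

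Cost: a few extra questions on calls already planned, at most one chart check or call per patient, one added model, and two safety summaries to present instead of one. The primary test and sample size do not change.
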